4.1 Duration of Study

The patients will be under active treatment with neoadjuvant cetuximab followed by either concurrent cetuximab EBRT or cisplatin EBRT for approximately 3 months. Afterwards, they will be followed every 3 months for a minimum of 2 years.

We anticipate it will take 3 years to accrue and treat the patients, followed by a 2 year follow up period. Therefore, this protocol should be completed about 5 years after IRB approval.

5. Patient Selection Criteria

5.1 Inclusion Criteria

A patient is eligible for enrollment if all of the following inclusion criteria are met.

5.1.1 Histologically proven squamous cell carcinoma of the oropharynx, hypopharynx or larynx.

- 5.1.2 Stage III/IVa/b SCC by AJCC 7 criteria (advanced, but not metastatic)
- 5.1.3 Patients must give informed consent.
- 5.1.4 Patients must have an ECOG performance status ≤ 2 (Appendix B).
- 5.1.5 Patients must have normal organ and marrow function as defined below:
 - Platelets $\geq 100,000 / \mu\text{L}$
 - ANC $\geq 1,500 / \mu\text{L}$
 - Hemoglobin $> 8 \text{ g/dL}$ (use of transfusion to achieve this is acceptable)
 - Total bilirubin $< 2 \times$ institutional upper limit of normal (ULN)
 - AST(SGOT)/ALT(SGPT) $\leq 3 \times$ institutional ULN
 - Serum creatinine $< 2 \times$ institutional ULN or creatinine clearance $> 50 \text{ mL/min}$ as determined by 24 hour collection or estimated by Cockcroft-Gault formula

$$\text{CCr male} = \frac{[(140 - \text{age}) \times (\text{wt in kg})]}{[(\text{Serum Cr mg/dL}) \times (72)]}$$

$$\text{CCr female} = 0.85 \times (\text{CrCl male})$$

- 5.1.6 Estimated life expectancy of at least 12 weeks.
- 5.1.7 Negative pregnancy test, if applicable

5.2 Exclusion Criteria

A patient will not be eligible for this study if any of the following exclusion criteria are met.

- 5.2.1 Patients may not have received previous therapy for their head and neck SCC, including chemotherapy, radiation therapy, or surgery beyond biopsy.
- 5.2.2 Second primary malignancy. Exceptions are 1) patient had a second primary malignancy but has been treated and disease free for at least 3 years, 2) in situ carcinoma (e.g. in situ carcinoma of the cervix), 3) non-melanomatous carcinoma of the skin
- 5.2.3 Patients with metastatic disease beyond the neck and supraclavicular region will be excluded
- 5.2.4 Serious concomitant systemic disorders (including active infections) that would compromise the safety of the patient or compromise the patient's ability to complete the study, at the discretion of the investigator. This includes scleroderma.
- 5.2.5 Age < 18 years.
- 5.2.6 History of allergic reactions attributed to compounds of similar chemical or biologic composition to cetuximab or cisplatin or other agents used in the study.
- 5.2.7 Women who are pregnant, due to the teratogenic effects of radiation therapy and chemotherapy on the unborn fetus. Women of childbearing age must agree to undergo a pregnancy test prior to therapy and to use adequate contraception (hormonal or barrier method of birth control; abstinence) prior to study entry, for the duration of study participation and for 6 months after. Should a woman become pregnant or suspect she is pregnant while participating in this study, she should inform her treating physician immediately.

5.2.8 Patients with HIV infection are not automatically excluded, but must meet the following criteria: CD4 count is $> 499/\text{cu mm}$ and their viral load is $< 50 \text{ copies/ml}$. Use of HAART is allowed.

5.2.9 Due to a small incidence of cardiac related complications with cetuximab EBRT, patients who have had either myocardial infarction, coronary artery bypass graft, coronary artery stenting, hospital admission for heart related issues such as congestive heart failure or arrhythmia *within the last 3 months*, will not be allowed on protocol.

5.2.10 Grade 3-4 electrolyte abnormalities (CTCAE, v. 4):

- Serum calcium (ionized or adjusted for albumin) $< 7 \text{ mg/dl (1.75 mmol/L)}$ or $> 12.5 \text{ mg/dl (> 3.1 mmol/L)}$ despite intervention to normalize levels;
- Magnesium $< 0.9 \text{ mg/dl (< 0.4 mmol/L)}$ or $> 3 \text{ mg/dl (> 1.23 mmol/L)}$ despite intervention to normalize levels;
- Potassium $< 3.0 \text{ mmol/L}$ or $> 6 \text{ mmol/L}$ despite intervention to normalize levels;
- Sodium $< 130 \text{ mmol/L}$ or $> 155 \text{ mmol/L}$ despite intervention to normalize levels.

5.3 Inclusion of Women and Minorities

Women and minorities are welcome to participate.

5.4 Participation of Children

Children younger than 18 years of age are not eligible for this trial. SCC of the head and neck is exceedingly rare in this population, and they would be better treated on a pediatric protocol.

5.5 Sources or Methods of Recruitment

Patients will be recruited from Rutgers New Jersey Medical School – Newark, Doctors Office Complex and University Hospital.

5.6 Study Enrollment Procedures

A copy of the institution's IRB-approved informed consent document and written justification for any changes made to the informed consent for this protocol must be on file at the Cancer Institute of New Jersey's Office of Human Research Services (OHRS) before any participating institution may enter patients.

To register eligible patients on this study, each site will contact OHRS. Contact information will be provided at the time of site activation. The signed and dated eligibility checklist, completed signature page of the consent form and additional source documents if requested by OHRS will need to be provided. Once OHRS verifies eligibility, a unique patient study number will be issued. The patient will not be identified by name. This is the point that the patient is considered on study. **Patients must not start protocol treatment prior to registration.**

If a patient does not receive any protocol therapy, baseline data will be collected and submitted on the pre-study and follow-up electronic case report forms (eCRF). The reason for not starting protocol therapy will be documented in the "follow-up eCRF". Case report form completion instructions and training will be provided to each participating institution prior to study activation at the participating institution.

6. Study Parameters

| Evaluations | Pre-cetuximab | Weekly during neoadjuvant cetuximab | After neoadjuvant cetuximab and prior to starting radiation therapy | Weekly during radiation therapy | For first 2 months after radiation therapy | 3 months after radiation therapy is completed | Follow ups every 3 months after radiation therapy for 2 years | After locoregional or distant failure |
|---|--|--|---|---------------------------------|--|---|---|---------------------------------------|
| History ⁸ , tumor assessment | X ¹ (within 1 month of enrollment) | X ⁶ | X ¹⁶ | X ¹ | | X ¹ (within 1 month) | X ¹ (within 1 month) | X ¹ |
| Dental Assessment | | X (as early as possible, but can be done any time prior to start of RT) | | | | | | |
| Speech Therapy Assessment | | X (as early as possible but can be done any time before or during RT treatment) | | | | | | |
| PEG Tube Assessment | | X (This is done at treating physician's discretion, and can be done any time before or during RT) | | | | | | |
| Photo of rash at head, neck, upper torso put into EMR | X (1 month to 1 day prior to first cetuximab) | X | | | | | | |
| Incisional/core biopsy of tumor | X (1 month to 1 day prior to first cetuximab) | | X (any time during this interval) | | | | | X (within 2 months) |
| Biopsy of skin | X (1 month to 1 day prior to first cetuximab) | | X (any time during this interval) | | | | | |
| CBC, differential, platelets | X (within 1 month to 1 day prior to enrollment) | X | | X | | | | |
| Serum Chemistries ² | X (within 1 month to 1 day prior to enrollment) | X | | X | X (monthly for two times +- 2 weeks) | X (within 1 month) | | |
| Liver Enzymes ³ | X (within 1 month to 1 day prior to enrollment) | | X | | | | | |
| Pregnancy Test ⁴ | X (within 1 month to 1 | | | | | | | |

| | day prior to enrollment) | | | | | | |
|---------------------------------------|--------------------------|--|------------------------------|--|--|--------------------------------------|---|
| Radiographic Assessments ⁵ | X ⁵ | | X (CT neck w IV contrast) | | | X (PET/CT at 3 months +- 1 month) | X |

1. To include toxicity assessment, ECOG performance status, weight
2. Includes: Electrolytes, including serum magnesium, potassium, Calcium, BUN, Creatinine, Glucose,
3. Includes: Total and Direct. Bilirubin, AST/ALT, Alkaline Phosphatase, Albumin, Total Protein.
4. Women 18-55 who have not undergone menopause must have urine pregnancy test within 3 weeks of enrollment.
5. Radiographic assessment prior to enrollment will consist of PET/CT obtained no more than 2 months prior to enrollment. CT neck w IV contrast will be obtained within 2 weeks to 1 day prior to first dose of cetuximab.
6. Assessment of rash
7. Any time during that week

7. Treatment Plan

7.1 General Considerations

The experimental aspect of this protocol is in the neoadjuvant cetuximab. Once treatment response to neoadjuvant cetuximab is established, the administration of concurrent cetuximab EBRT (with the exception that the cetuximab loading dose has already been delivered) or cisplatin EBRT is standard. The protocol may be divided into the following phases:

7.2 Sequence of treatment

7.2.1 Prior to neoadjuvant cetuximab

Patients will be staged using PET/CT to delineate the extent of disease. Preferably, they would receive PET/CT with IV contrast so that the CT may be used to assess response to cetuximab (CT without IV contrast is not adequate for assessing the tumor or lymph nodes). In case the staging PET/CT has already been done, a CT neck with IV contrast will be ordered prior to receiving neoadjuvant cetuximab, so that the RECIST 1.1 criteria may later be applied. In case the patient cannot receive PET/CT due to insurance issues, CT neck and chest with IV contrast may be substituted.

Initial biopsy specimen (incisional/core biopsy as opposed to a FNA) will be procured from the head and neck (primary site) and punch biopsy obtained from the skin. As tissue from

the head and neck and skin will be used for DNA and RNA genotyping, tissue that is preserved and sufficient in quantity is required. So even if a patient has had a previous biopsy that is paraffin encased, a repeat biopsy may be obtained. These specimens will be handled as delineated in section 11.3.

All patients will be referred for dental evaluation. If any dental extractions are required, they should be performed early in the course (1st week preferably) of neoadjuvant cetuximab, so that radiation therapy is not delayed. Patients may be referred for PEG if appropriate. PEG should be placed during the course of neoadjuvant cetuximab or early in the course of radiation therapy, so that there is minimal esophageal mucositis at the time of PEG placement.

7.2.2 Neoadjuvant Cetuximab

Patients who agree and are eligible for this protocol will initially receive 3 weeks of neoadjuvant cetuximab. The initial dose of cetuximab will be 400 mg/m² IV, followed by 2 weekly doses of cetuximab 250 mg/m² IV. Those patients who are responders will then continue the weekly doses of cetuximab until the radiation therapy is completed.

Patients will not receive prophylactic antibiotics prior to initiating cetuximab, so that the rash may be accurately assessed. After three weeks of neoadjuvant cetuximab or after the presence of cetuximab related folliculitis (and therefore their inclusion in the cetuximab EBRT cohort) is established, antibiotics may be prescribed. Even if a patient is found to have a cetuximab related folliculitis, they will complete the scheduled 3 weeks of neoadjuvant cetuximab.

7.2.3 Assessing for response during and after neoadjuvant cetuximab

The criteria for a positive response to cetuximab will be either 1) development of cetuximab related folliculitis or 2) CT response by RECIST 1.1 criteria. CT progression will constitute a negative response to cetuximab, regardless of folliculitis.

7.2.3.1 Cetuximab related Folliculitis

After each week of cetuximab, the patient will be assessed by medical oncology and radiation oncology for development of folliculitis characteristic of EGFR inhibition, a photo of the face and upper trunk taken and placed in their electronic medical record. Note that such photos have in the past not been routine, as nothing was done with rash information, though taking pictures of any unusual clinical features is routine (for example, cancers invading into skin). These photos will be taken by the PI, his designate or OHRS staff with a camera dedicated to taking patient pictures (not just for this protocol, but also for radiation setup checks) in the respective radiation departments, and will be put into the EMR systems (Mosaic at Rutgers New Jersey Medical School and aria at Rutgers Robert Wood Johnson Medical School). These EMR systems are password protected, and so these pictures remain confidential.

Though the rash associated with EGFR inhibition appears similar to acne vulgaris and is commonly referred to as acne, acne-like, or acneiform, these terms are technically

inaccurate. Unlike acne vulgaris, which is characterized clinically by both noninflammatory lesions known as comedones (blackheads and whiteheads) as well as inflammatory papules, pustules, and nodules, EGFR-associated rash is dominated by pustules that contain an intrafollicular collection of neutrophils—the hallmarks of an infectious folliculitis. Per Perez-Soler, the typical EGFR associated rash has a clinical presentation characterized by pustular/papular appearance, usually involving the face, head, and upper torso, and often accompanied by pruritus, dry skin, and erythema³⁰

In previous reports, the criteria used for significant EGFR associated rash has most commonly been grade 2+ on the CTCAE 3.0 criteria listed below. The problem with this criteria is that much of it is very subjective i.e., when exactly is intervention indicated for a rash/acne/acneiform, or how much pruritis is necessary to be intense or widespread and how can one measure pruritis beyond asking the patient how bad it is?

CTCAE 3.0 Criteria (not used in this protocol)

| | 1 | 2 | 3 | 4 |
|----------------------------|---|---|---|---|
| Pruritus/itching | Mild or localized | Intense or widespread | Intense or widespread and interfering with ADL | - |
| Rash/desquamation | Macular or papular eruption or erythema without associated symptoms | Macular or papular eruption or erythema with pruritus or other associated symptoms; localized desquamation or other lesions covering < 50% of body surface area (BSA) | Severe, generalized erythroderma or macular, papular or vesicular eruption; desquamation covering > 50% BSA | Generalized, exfoliative, ulcerative, or bullous dermatitis |
| Rash/acne/acneiform | Intervention not indicated | Intervention indicated | Associated with pain, disfigurement, ulceration, or desquamation | - |
| Nail changes | Discoloration; Ridging (koilonychias); pitting | Partial or complete loss of nail(s); pain in nail bed(s) | interfering with ADL | - |

Therefore, we chose folliculitis criteria with the goal of making it objective and reproducible, in case this protocol were to someday be expanded to a phase II or III trial. We recognize that the cost of this folliculitis criteria may be that some patients who may have had a significant rash per CTCAE 3.0 criteria may not be considered responders here; however, subjective response criteria would severely limit the value of this protocol in the future. With this in mind, the criteria for development of cetuximab related folliculitis is:

Development of folliculitis characterized by a pustular/papular appearance located on the face, head, or upper torso (examples in appendix C).

7.2.3.2 CT response by RECIST 1.1 criteria

The week after the 3rd dose of neoadjuvant cetuximab (Day 14-21 after the first dose of cetuximab), the patient will have a CT neck with IV contrast for comparison to the first CT neck performed prior to neoadjuvant cetuximab. CT response will be evaluated using RECIST 1.1 criteria: (E.A. Eisenhauer et al. New response evaluation criteria in solid tumours: Revised RECIST guideline (version 1.1). EUR J CANCER 45 (2009) 228-247].

Evaluation of Target Lesions

| | |
|---------------------------|---|
| Complete Response (CR): | Disappearance of all target lesions. Any pathological lymph nodes (whether target or non-target) must have reduction in short axis to <10 mm. |
| Partial Response (PR): | At least a 30% decrease in the sum of diameters of target lesions, taking as reference the baseline sum diameters. |
| Progressive Disease (PD): | At least a 20% increase in the sum of diameters of target lesions, taking as reference the smallest sum on study (this includes the baseline sum if that is the smallest on study). In addition to the relative increase of 20%, the sum must also demonstrate an absolute increase of at least 5 mm. (Note: the appearance of one or more new lesions is also considered progression). |
| Stable Disease (SD): | Neither sufficient shrinkage to qualify for PR nor sufficient increase to qualify for PD, taking as reference the smallest sum diameters while on study |

Please note that significant changes from version 1.0 include for malignant lymph nodes: To be considered pathologically enlarged and measurable, a lymph node must be >15mm in short axis when assessed by CT scan (CT scan slice thickness recommended to be no greater than 5 mm). At baseline and in follow-up, only the short axis will be measured and followed.

7.2.4 Repeat Bx after neoadjuvant cetuximab. After 3 weeks of neoadjuvant cetuximab, a biopsy specimen (incisional/core biopsy as opposed to a FNA) will be procured from the head and neck primary site). As this tissue will be used for DNA and RNA sequencing, tissue that is preserved and sufficient in quantity is required. These specimens will be handled as delineated in 11.3.

7.2.5 Determining treatment modality

The patients who receive cisplatin RT will be those who

1. progress by CT RECIST 1.1 criteria during neoadjuvant cetuximab, regardless of rash
2. do not develop either a cetuximab related folliculitis or a partial response by CT RECIST 1.1 criteria

The patients who receive cetuximab RT will be those who

1. develop a cetuximab related folliculitis (at any point following the first cetuximab dose and prior to starting EBRT) without CT progression (ie stable or partial response)
2. have at least a partial response by CT RECIST 1.1 criteria

The dependence of treatment modality on CT response and rash is illustrated by the below table:

CT response by RECIST 1.1

| | Progressive disease | Stable disease | Partial response |
|------|------------------------------------|----------------|------------------|
| Rash | (-) cetuximab related folliculitis | Cis RT | Cetux RT |
| | (+) cetuximab related folliculitis | Cis RT | Cetux RT |

7.2.6 Concurrent cetuximab and EBRT

Patients receiving cetuximab EBRT will receive concurrent cetuximab 250 mg/m² IV weekly during the duration of EBRT. There will be no breaks in weekly cetuximab delivery i.e., patients will receive weekly cetuximab from the first dose of neoadjuvant cetuximab to the end of radiation therapy (except when discontinued for toxicity). Patients will be seen and assessed weekly by radiation oncology and medical oncology.

7.2.7 Concurrent cisplatin and EBRT

Patients receiving concurrent cisplatin EBRT will receive 100 mg/m² q 3 weeks during EBRT or alternatively, 40 mg/m² weekly during EBRT. The q 3 weeks regimen is preferable, but the weekly regimen may also be used, at the discretion of the treating medical oncologist. The EBRT technique will be identical to that used for concurrent cetuximab and EBRT. Patients will be seen and assessed weekly by radiation oncology and on a regular basis by medical oncology, how frequently depending on the cisplatin regimen.

7.3 External Beam Radiation Therapy

The EBRT will be performed either at Rutgers New Jersey Medical School - Newark or RWJUH radiation oncology, using either 3 dimensional conformal radiation therapy (3DCRT) or intensity modulated radiation therapy (IMRT). Tomotherapy is considered a form of IMRT. IMRT will be performed using 3 different dose levels applied to 3 target volumes: PTV1 (70 Gy in 33 fractions), PTV2 (60 Gy in 33 fractions) and PTV3 (54 Gy in 33 fractions). 100% of the dose will be prescribed to at least 95% of the PTV volume.

Tolerances for normal structures will be observed at the following limits:

| | |
|----------------------|---------------|
| Brainstem + 0.5 cm | maximum 54 Gy |
| Spinal cord + 0.5 cm | maximum 50 Gy |

| | |
|-----------|---------------|
| Mandible | maximum 70 Gy |
| Parotids* | mean 26 Gy |

*Parotids will be spared depending on proximity to pathologic lymph nodes

In certain cases, the location of the tumor will make these limits impossible to achieve, and patients will be planned at the discretion of the treating radiation oncologist.

7.3.1 Dose Modifications or Escalations

Treatment breaks will be granted only in case of severe grade 3 / 4 toxicity per the discretion of the treating radiation oncologist.

7.3.2 Hematologic Toxicity

The amount of bone marrow affected by head and neck radiation therapy is very small, and has minimal effect on hematologic toxicity. Radiation therapy will not routinely be held for hematologic toxicity, except at the discretion of the treating radiation oncologist.

7.3.3 Non-Hematologic Toxicity

7.3.3.1 Mucositis. Patients may require analgesia with narcotic agents during and after radiation therapy. They will be started on short acting agents such as oxycodone or percocet and may require long acting medication such as Oxycontin or fentanyl patch as well. They may also receive other soothing mouthwash prescriptions. Patients will be encouraged to have a PEG placed prior or early in the course of radiation therapy, though failure to do so will not exclude them from this protocol.

7.3.3.2 Change in Taste

This is an expected side effect and patients will be advised accordingly that despite change in taste, that they must continue to take in sufficient calories to maintain their weight as much as possible.

7.3.3.3 Dry mouth. Patients will be encouraged to use frequent baking soda and water mouth rinses as well as mouth moisturizing products like Biatene spray.

7.3.3.4 Skin reaction. Patients will be encouraged to apply Vaseline based cream such as aquaphor on neck at least twice daily.

7.3.4 Adherence/Compliance

Patients who do not adhere to their radiation oncologists recommendations regarding daily radiation treatments may be removed from the study.

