1.1 Primary Endpoint

The primary endpoint is 2 yr locoregional control in cetuximab responders. Our hypothesis is that patients who respond to neoadjuvant cetuximab and go on to receive concurrent cetuximab RT will have improved 2 yr locoregional control compared to unselected patients who receive cetuximab RT ie the cetuximab RT arm in the seminal Bonner randomized trial. The Bonner trial randomized advanced HNSCC to RT alone versus cetuximab RT.¹ The patients in the cetuximab arm were completely unselected, and had a 2 yr LRC of 50%. In the update, he noted that of the cetuximab treated patients, development of a significant rash (folliculitis) had a huge prognostic impact, with significant rash patients having a OS more than twice as long as no significant rash patients (68.8 months vs 25.6 months; HR 0.49, 0.34–0.72; p=0.002).²

Our hypothesis is that if patients are selected by response to neoadjuvant cetuximab, that those patients will have at least a 25% improved LRC over those historical cetuximab patients who were unselected. Given the difference that rash appears to make, we feel this is a very reasonable estimate.

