7.4.6 Adherence/Compliance

Patients will receive weekly cetuximab per their medical oncologist. They should adhere to their oncologist's recommendations (based on the protocol) re administration of cetuximab. Failure to do so may result in removal from the study.

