9.2 Evaluation of CT response at primary site and neck

CT scans of the neck with IV contrast will be taken before and after neoadjuvant cetuximab (Day 14-21 after the first dose of cetuximab). At the primary site and neck lymph nodes, the largest diameter on axial CT slices will be measured and recorded. All measurements will be taken and recorded in metric notation using measuring software in the applicable radiology programs. In all possible cases, spiral CT (as opposed to standard CT) will be performed. Response will be graded per RECIST 1.1 criteria: [E.A. Eisenhauer et al. New response evaluation criteria in solid tumours: Revised RECIST 1.1 guideline (version 1.1). Eur J Cancer 45 (2009) 228-247].

Evaluation of Target Lesions

| | |
|---------------------------|---|
| Complete Response (CR): | Disappearance of all target lesions. Any pathological lymph nodes (whether target or non-target) must have reduction in short axis to <10 mm. |
| Partial Response (PR): | At least a 30% decrease in the sum of diameters of target lesions, taking as reference the baseline sum diameters. |
| Progressive Disease (PD): | At least a 20% increase in the sum of diameters of target lesions, taking as reference the smallest sum on study (this includes the baseline sum if that is the smallest on study). In addition to the relative increase of 20%, the sum must also demonstrate an absolute increase of at least 5 mm. (Note: the appearance of one or more new lesions is also considered progression). |
| Stable Disease (SD): | Neither sufficient shrinkage to qualify for PR nor sufficient increase to qualify for PD, taking as reference the smallest sum diameters while on study |

Please note that significant changes from version 1.0 include for malignant lymph nodes: To be considered pathologically enlarged and measurable, a lymph node must be >15mm in short axis when assessed by CT scan (CT scan slice thickness recommended to be no greater than 5 mm). At baseline and in follow-up, only the short axis will be measured and followed.

10. Removal of Patients from Study/Off Study Criteria

In the absence of treatment delays due to adverse events, treatment may continue until one of the following criteria applies:

- a) Intercurrent illness that prevents further administration of treatment,
- b) Patient decides to withdraw from the study,
- c) Noncompliance with treatment plan,

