16.1 Primary Hypothesis

The primary hypothesis is that patients who respond to neoadjuvant cetuximab and go on to receive concurrent cetuximab RT will have improved 2 yr locoregional control compared to unselected patients who receive cetuximab RT ie the cetuximab RT arm in the seminal Bonner randomized trial.

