16.4 Outcome Measures

The main outcome measure is 2 yr locoregional control in cetuximab responders.

Secondary outcomes include percent of patients who progress during 3 weeks of neoadjuvant cetuximab by CT RECIST 1.1 criteria, and 2 yr locoregional control for non-responders to neoadjuvant cetuximab.

Other outcomes are molecular correlates. The study is powered only for the main outcome measure. Secondary outcome measurements are descriptive.

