16.7 Compliance and Missing Data

Compliance is defined as adhering to the protocol treatment plan, follow up imaging and appointments for at least 2 years following radiation therapy.

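### Responders who do not adhere to radiation or cetuximab may be removed from the study, and the plan fixes neither their follow-up nor the primary analysis set

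*Combined protocol and SAP*

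**What the plan says.** **Removal.** Two rules can reach the primary cohort. Section 7.3.4 (radiation) states that "Patients who do not adhere to their radiation oncologists recommendations regarding daily radiation treatments may be removed from the study". Section 7.4.6 (cetuximab) asks patients to follow their oncologist's recommendations and adds "Failure to do so may result in removal from the study". Section 7.5.6 has the same rule for cisplatin, which goes to non-responders and so bears only on the secondary LRC outcome.

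**Off-study criteria.** Section 10 lists "Noncompliance with treatment plan" under a heading about removal from study. Its lead sentence, however, speaks only of how long treatment may continue.

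**Compliance and missing data.** The whole of section 16.7 is one sentence: "Compliance is defined as adhering to the protocol treatment plan, follow up imaging and appointments for at least 2 years following radiation therapy". It attaches no consequence to non-compliance and gives no missing-data rule.

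**Population.** Section 16.1 frames the hypothesis for "patients who respond to neoadjuvant cetuximab and go on to receive concurrent cetuximab RT"; sections 1 and 1.1 word it similarly. The endpoint in section 1.1 reads "The primary endpoint is 2 yr locoregional control in cetuximab responders", and section 16.4 reads "The main outcome measure is 2 yr locoregional control in cetuximab responders". The reporting list in section 16.5 and the sample size in section 16.2 also refer to cetuximab responders, with no condition on later treatment.

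**Evaluability.** Section 8 says who is evaluable for toxicity. No section does this for efficacy.

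**The concern.** Removal from the study is a different event from stopping protocol treatment. A patient who stops treatment can still be scanned and counted at two years; a patient who leaves the study may be neither. The plan does not separate the two, and it allows removal at the discretion of people who can see how the patient is doing.

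The two descriptions of the population make this worse. A responder who starts but does not complete cetuximab RT, or never starts it, belongs to the endpoint population of sections 1.1 and 16.4 but arguably not to the hypothesis population of section 16.1. Nothing says which governs, so the choice could be made after outcomes are known.

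The design is sensitive to this. It is a single arm with no concurrent control in which similar exclusions might offset the effect, the test is one-sided against a fixed historical 50%, and about 16 patients carry the result. Section 16.2 assumes no loss to follow-up, while sections 7.3.4 and 7.4.6 permit loss.

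**Working it through.** **Inputs (section 16.2).** Two-year LRC 50% under the null and 75% under the alternative; one-sided 5% level; 80% power; exponential event times; uniform accrual over 3 years plus 2 years of follow-up; no loss; 16 responders; 60% response; 27 patients.

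**The plan's own figure.**
- Hazards per year: λ0 = −ln(0.50)/2 = 0.3466 and λ1 = −ln(0.75)/2 = 0.1438.
- Probability of an observed event: p = 1 − (e^(−2λ) − e^(−5λ))/(3λ), which gives p0 = 0.689 and p1 = 0.391.
- On the log-hazard scale: n = [(1.645/√0.689 + 0.842/√0.391) / ln(0.3466/0.1438)]² = [(1.982 + 1.346)/0.879]² = 14.3, so 15, with 83% power at 16.
- The plan does not name the scale; on the raw hazard scale n is 19. The stated 16 is consistent with an exponential test of this kind.
- Total: 16/0.60 = 26.7, so 27, as stated.

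The sample size is not in dispute. What follows measures sensitivity to removals.

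**Observed LRC if failures are lost.** With 16 responders and a true LRC of 50%, 8 are controlled and 8 fail.

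| 2-year failures lost | Observed LRC |
|---|---|
| 0 | 8/16 = 50% |
| 1 | 8/15 = 53% |
| 2 | 8/14 = 57% |

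**False-positive rate.** I took the planned test to be a one-sample log-rank test against λ0: Z = (O − E)/√E, where E is the sum of λ0 × follow-up time, rejecting when Z < −1.645. Event times were simulated at λ0 with follow-up uniform between 2 and 5 years, at least 200,000 runs per case. The patients lost were drawn at random from those failing within two years.

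| Handling | 1 patient | 2 patients |
|---|---|---|
| Failures deleted | about 5.9% | about 9.4% |
| Failures censored at 3 months (failures before then still counted) | about 5.6% | about 8.6% |
| Patients removed regardless of outcome | about 3.6% | about 3.5% |

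With nobody removed the rate is 3.6%. Two things follow. Inflation appears only when removal is related to failure. And censoring the removed patients, instead of deleting them, does not cure it.

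**Direction.** If a share d of responders is removed and their failure risk is f, the LRC among the rest is (0.50 − d(1 − f))/(1 − d). The documents give neither d nor f, so the values below are assumptions.

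| d | f = 25% | f = 50% | f = 75% | f = 100% |
|---|---|---|---|---|
| 10% | 47.2% | 50.0% | 52.8% | 55.6% |
| 20% | 43.75% | 50.0% | 56.25% | 62.5% |

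For example, d = 10% and f = 25% gives (0.50 − 0.075)/0.90 = 47.2%.

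**The case against.** The other side has a fair case. Removal is optional wherever it appears. No text takes a removed patient out of the denominator. Section 4.1 plans at least two years of follow-up for patients generally, section 5.6 requires follow-up forms even for a registered patient who never starts therapy, and section 13.2 keeps a research chart for every enrolled patient. The endpoint, outcome measure, reporting list and sample size all speak of cetuximab responders, so the hypothesis wording may simply describe the planned pathway. In a pilot of 27 patients this could be called a matter of wording.

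Much of that stands, and it rules out several stronger readings:

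- **Missed follow-up as a ground for removal.** A reader might infer this by combining sections 16.7 and 10. The documents do not support it: section 16.7 only defines compliance, and section 10 refers to the treatment plan.
- **Section 10 as a clear removal rule.** Its heading suggests that, but its operative sentence concerns treatment. It is ambiguous at most.
- **Established upward bias.** Nothing in the documents shows that patients who miss radiation or cetuximab fail more often than the rest.
- **A false-positive rate of 12.5% with two failures lost.** That figure arises only if the remaining 14 patients are given a constant hazard matching 57.1% at two years. This also lowers their hazard after year two, which losing early failures does not do. Deleting the failures directly gives about 9.4%.

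What the objection does not supply is a statement that removed responders stay in LRC follow-up and in the primary analysis. The general follow-up provisions do not address patients who have been removed, and the two population wordings remain unreconciled.

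**Conclusion.** The concern holds as a gap in the analysis plan with a specific and inexpensive remedy. Responders who do not adhere to radiation or cetuximab may be removed from the study, their later follow-up and analysis are undefined, and the hypothesis and endpoint describe different populations. It is not an error in the sample size, nor evidence that the result will be biased.

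The size is conditional on how many responders are removed and how often they fail. If one or two 2-year failures are lost from 16 responders at a true LRC of 50%, the false-positive rate moves from about 3.6% to about 5.9% or 9.4%, above the nominal 5% in both cases. If removal is unrelated to outcome there is no inflation, and if removed patients do better than the rest the estimate is biased downward. These rates also assume exponential event times and a one-sample log-rank test against the hazard implied by 50% at two years. Since the direction cannot be known in advance, the set should be fixed before any outcome is seen. I would class this as a cheap improvement.

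**What to change.** - **Sections 7.3.4, 7.4.6 and 10:** distinguish leaving protocol treatment from leaving the study. State that a patient taken off protocol treatment continues LRC follow-up on the section 6 calendar unless consent is withdrawn. Make the same change in 7.5.6 to protect the secondary LRC outcome in non-responders. The rules on who stops treatment need not change.
- **Sections 16.1, 16.4 and 16.5:** define the primary set as every patient classified as a cetuximab responder under section 7.2.5, whatever treatment follows. Present the treated-as-planned set only as a sensitivity analysis. Align the hypothesis wording in sections 1 and 1.1.

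The cost is some protocol wording, routine follow-up of a few more patients, and possibly a slightly less favourable LRC estimate.
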